7.2.5 Cessation Phase – Phone Call #2 (Day 21 ± 3 days)

During this phone contact, daily nicotine cigarette/film diary information will be collected, adverse events or changes to concomitant medications will be documented, and participants will be asked to verbally answer the measures indicated in the Time and Events Table during the phone call. Participants' answers will be entered directly into REDCap by the researcher at the time of the call.

7.2.6 Cessation Phase – Visit 4 (Day 28 ± 3 days)

At this in-person visit, the following procedures will be conducted:

- 7.2.6.1** Adverse events will be documented, and any concomitant medication changes will be recorded.
- 7.2.6.2** The daily cigarette/film diary will be collected and recorded by the researcher. Use of other tobacco products in the past 7 days will also be assessed.
- 7.2.6.3** Participants will complete the measures and study procedures indicated in the Time & Events Table.

- 7.2.6.4** All nicotine pouches from the previous weeks (unopened, opened, or empty) will be collected by the researcher
- 7.2.6.5** Participants will be provided with a new supply of their assigned nicotine films (14-day plus 3-day supply [68 films total]) to use over the next two weeks until their next study visit.
- 7.2.6.6** Participants will be asked to return all used (opened/empty) and unused (unopened) study product pouches at their next study visit.
- 7.2.6.7** Participants will be encouraged to remain abstinent from cigarettes.
- 7.2.6.8** Participants will be instructed to continue to maintain a daily diary of their nicotine film use. This diary will require that they record the time of day each film was taken. Participants will be instructed to only record cigarettes smoked on their diary in the event that they experience a slip.
- 7.2.6.9** Participants will be compensated for completing the study visit and procedures.

7.2.7 Cessation Phase – Phone Call #3 (Day 35 ± 3 days)

During this phone contact, daily cigarette/film diary information will be collected, adverse events or changes to concomitant medications will be documented, and participants will be asked to verbally answer the measures indicated in the Time and Events Table during the phone call. Participants' answers will be entered directly into REDCap by the researcher at the time of the call.

7.2.8 Cessation Phase – Visit 5 (Day 42 ± 3 days)

At this in-person visit, the following procedures will be conducted:

- 7.2.8.1** Adverse events will be documented, and any concomitant medication changes will be recorded.
- 7.2.8.2** The daily cigarette/film diary will be collected and recorded by the researcher. Use of other tobacco products in the past 7 days will also be assessed.
- 7.2.8.3** Participants will complete the measures and study procedures indicated in the Time & Events Table.
- 7.2.8.4** All nicotine pouches from the previous weeks (unopened, opened, or empty) will be collected by the researcher
- 7.2.8.5** Participants will be encouraged to remain abstinent from cigarettes.
- 7.2.8.6** Participants will be compensated for completing the study visit and procedures.

7.2.9 Study Visit Reminders

Phone calls and/or text messages will be used throughout the study to remind participants of their next visits (approximately 1-2 days prior) (SEE VISIT SCRIPT ATTACHMENT). Also, visit time/date confirmation and study center directions will be emailed/mailed to the participant prior to Visit 1 (SEE FIRST VISIT REMINDER ATTACHMENT).

7.3 Duration of Participation

Participants who complete the entire study will participate in the study for 7 weeks.

7.4 Test Article(s) (Study Drug(s) and/or Study Device(s))

7.4.1 Description

Nicotine orally dissolving films will be provided in doses of 0, 2, or 4 mg. The active pharmaceutical ingredient in these nicotine films is nicotine polacrilex (20%, USP). The film used in has a muco-adhesive property (i.e., it can adhere to the oral mucosa and allow the drug to be absorbed through oral mucosa). After placement in the oral cavity, the nicotine film dissolves over a 5 minute period. The unit-dose dosage is in the form of a 1 in x 1 in square and weighs

about 100 mg. Nicotine films are not available in the United States in a non-investigational setting. See table below for composition information.

Nicotine ODF Dosage		0 mg	2 mg	4 mg
Material Name	Grade	Weight, g	Weight, g	Weight, g
Sodium Bicarbonate	USP/EP	1.97	1.71	1.64
Propylene Glycol	USP/EP	23.66	20.55	19.68
Nicotine Polacrilex 20%	USP	0.00	17.81	37.72
Purified Water	USP	209.04	205.45	196.80
Ethanol anhydrous	USP	110.44	119.85	114.80
Polyox N10 (Polyethylene oxide)	NF	134.10	116.42	111.52
Saccharin	Food Grade	2.45	2.12	2.03
Cocoa Powder	Food Grade	1.77	1.71	1.97
L-Menthol	USP	9.98	8.66	8.30
Peppermint oil	USP	6.19	5.38	5.15
Methylparaben	NF	0.20	0.17	0.20
Propylparaben	NF	0.20	0.17	0.20
Total		500.00	500.00	500.00

7.4.2 Treatment Regimen

Nicotine films will be administered orally. They are used by placing a film on the tongue, closing the mouth, and pressing the tongue gently to the roof of the mouth. The film will dissolve in the mouth within 5 minutes. Three doses of nicotine film will be used in this study: 0, 2, and 4 mg.

Participants will be randomized to one of three possible treatment regimens:

- 1) **Random nicotine delivery** (a combination of four 0 mg and 4 mg films daily not to exceed three non-consecutive 4 mg films in one day and to maintain an average of 8mg of nicotine per day through 7 days for 6 weeks total)
 - a) Possible weekly random delivery dosing scenarios to maintain an 8 mg/day average through 7 days:
 - a. One 4mg day, five 8mg days, and one 12mg day in any order
 - b. Two 4mg days, three 8mg days, and two 12mg days in any order

Possible Daily Sequences for Random Delivery		
4mg/day	8mg/day	12mg/day
4000	4400	4404
0400	4040	4044
0040	4004	
0004	0440	
	0404	
	0044	

- 2) **Steady state nicotine delivery** (2, 2, 2, 2 mg films daily for 6 weeks total)
- 3) **Placebo delivery** (0, 0, 0, 0 mg films daily for 6 weeks total)

Participants will be directed to take one film every 3-4 hours, in a specified order, for a total of four films consumed daily. In the event that participants miss taking a scheduled film, they will be instructed to skip the film if more than 8 hours has passed since they took their last film. They will be asked to indicate on their daily diary if a film was missed..

7.4.3 Method for Assigning Subject to Treatment Groups

Participants will be randomized to one of three dosing groups based on a predetermined random number sequence generated by the study statistician, [name] [name].

7.4.4 Subject Compliance Monitoring

Participants will be given a paper daily diary to complete on which they will record: 1) the number of cigarettes smoked each day, and 2) the date and time of each nicotine film taken. Participants will be given detailed instructions on how to complete the diary. Questions will be asked at each contact to review participants' logs and to verify their daily conventional cigarette and nicotine film use. Participants will also be asked to self-report their other tobacco use at each visit, including use of products such as electronic cigarettes, cigars, pipes, chew, snus, dip, hookah, and dissolvable tobacco. Exhaled carbon monoxide measurements will be collected throughout the study to verify smoking intensity.

Participants will be asked to return all of their used (empty/opened) and unused (unopened) nicotine film pouches to each study visit following Visit 2. At each of these visits, study staff will document the number of used and unused nicotine film pouches to verify participants' film use and compliance.

7.4.5 Blinding of the Test Article

Blinded packages of the nicotine films will be created for each participant by an unblinded pharmacy staff member. Both the participant and the researcher will be blinded to the assigned dosing regimen and to the doses of each film.

7.4.6 Receiving, Storage, Dispensing and Return

7.4.6.1 Receipt of Test Article

The nicotine films will be manufactured by Bionex Pharmaceuticals, LLC in its North Brunswick, NJ facility under cGMP conditions and shipped directly to Penn State Hershey Medical Center. The packaged test article has been tested to be stable at temperatures up to 30°C for 12 months, and therefore, will be shipped via courier under room temperature.

Each nicotine film will be individually packaged in a sealed, chemical- and moisture-resistant, multi-component (polyester/aluminized), laminated pouch.

7.4.6.2 Storage

The nicotine films will be stored in the Investigational Drug Services (IDS) Pharmacy at the Penn State Milton S. Hershey Medical Center in accordance with guidelines provided by the manufacturer.

7.4.6.3 Preparation and Dispensing

The nicotine films will arrive in individually sealed, peel-apart pouches. They will be blinded by pharmacy staff who will appropriately package kits containing each daily nicotine film dosing regimen to last the participant until the end of their next study visit window. The four individual films within each daily regimen's container will be numbered so that the films are taken in the appropriate sequential order each day. The blinded researchers will not be involved in the packing and labeling of the kits. All receiving, sorting, blinding of the study product will be done in IDS pharmacy space at Penn State.

7.4.6.4 Return or Destruction of the Test Article

Participants will be required to return all study products to the research center at each clinic visit, including any empty/opened pouches using provided containers/bags. Any remaining nicotine films will be destroyed according to Penn State IDS Pharmacy protocol at the conclusion of the study.

7.4.6.5 Prior and Concomitant Therapy

Concomitant medication use will be collected at baseline and regularly throughout the study to serve as covariates during analysis and to monitor participant health conditions. Participants currently using FDA approved cessation medications will be excluded. Should a participant start a medication during the randomized, double-blind phase of the study that would interfere with their ability to participate, they may be withdrawn from the study.

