1.0 Objectives

1.1 Study Objectives

The objective of this study is to determine whether treatment with random nicotine delivery via nicotine film both before and after the quit date will facilitate cessation relative to treatment with steady state delivery or placebo. We hypothesize that smoking cessation will be greater in subjects assigned to a random nicotine delivery regimen (as compared to those assigned to a steady state or placebo regimen). The nicotine film product is not part of the standard of care and is not available in non-investigational settings in the United States.

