1.2 Primary Study Endpoints

The primary endpoints for the study include the percent reduction in the number of cigarettes smoked and the accompanying percent reduction in exhaled carbon monoxide (CO) levels.

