7.2.4 Cessation Phase – Visit 3 (Day 14 ± 3 days)

At this in-person visit, the following procedures will be conducted:

- 7.2.4.1** Adverse events will be documented, and any concomitant medication changes will be recorded.
- 7.2.4.2** The daily cigarette/film diary will be collected and recorded by the researcher. Use of other tobacco products in the past 7 days will also be assessed.
- 7.2.4.3** Participants will complete the measures and study procedures indicated in the Time & Events Table.
- 7.2.4.4** All nicotine pouches from the previous weeks (unopened, opened, or empty) will be collected by the researcher.
- 7.2.4.5** Participants will be provided with a new supply of their assigned nicotine films (14-day plus 3-day supply [68 films total]) to use over the next two weeks until their next study visit.
- 7.2.4.6** Participants will be asked to return all used (opened/empty) and unused (unopened) study product pouches at their next study visit.
- 7.2.4.7** Participants will be instructed to cease all cigarette use and to only use their assigned nicotine films beginning the next morning.
- 7.2.4.8** Participants will be provided with the document from the Centers for Disease Control and Prevention titled, "A Report of the Surgeon General: How Tobacco Smoke Causes Disease." Participants will also be given a document with tips to prepare and succeed in a quit attempt.
- 7.2.4.9** Participants will be instructed to continue to maintain a daily diary of their nicotine film use. This diary will require that they record the time of day each film was taken. Participants will be instructed to only record cigarettes smoked on their diary in the event that they experience a slip.
- 7.2.4.10** Participants will be compensated for completing the study visit and procedures.

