8.3 Statistical methods

Paired sample t-tests (or nonparametric Wilcoxon Rank-Sum tests) will be used to examine changes in the outcome measures (CPD, CO, subjective measures, BP, HR) from baseline.

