11.0 Risks

Potential risks for subjects are minimal. We have previously tested both single and repeat administration of each of the nicotine film doses which will be dispensed to subjects. We found that they were well-tolerated by subjects and produced nicotine levels in the blood that are less than subjects routinely receive from their cigarette smoking.¹⁹ Subjects will have a review of their medical history prior to entry into the study. Subjects will be under medical supervision throughout their participation in the study, and adverse symptoms will be recorded by the research staff and monitored by the medical monitor and PIs. The major risks associated with the study are related to the use of nicotine (which is similar to the nicotine received from smoking) and nicotine withdrawal.

Additional potential risks include:

- **Nicotine film side effects:** Excess nicotine can cause mild symptoms such as nausea, dizziness, diarrhea, rapid heartbeat, heartburn, and hiccups. Occasionally these symptoms are more severe (e.g., vomiting) such as when an individual receives more nicotine than they are accustomed to. This, however, is unlikely to occur with the doses used in this study.
- **Nicotine withdrawal symptoms:** Ceasing conventional cigarette use may result in nicotine withdrawal symptoms (e.g., irritability, anxiety, restlessness, depressed mood, increased appetite, fatigue, difficulty concentrating). These symptoms will be monitored at each visit. Those receiving placebo films may experience more serious nicotine withdrawal symptoms.
- **Risk to fetus and breast fed infants:** Nicotine is known to be harmful to the developing human fetus, either from cigarettes or at the dose being used in this study. Women who are pregnant or are nursing a child may not participate in this research study. Women capable of becoming pregnant will be administered a pregnancy test prior to beginning the research. Participants must agree to take reasonable and necessary precautions against becoming pregnant during the period of the investigation.
- **Loss of confidentiality:** There is a risk of loss of confidentiality if information is obtained by someone other than the investigators. Precautions will be taken to prevent this including direct coding of data in REDCap.
- **Randomization:** Participants will be assigned to a treatment program by chance. The research intervention they receive may prove to have more side effects than the other research intervention(s).

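### Section 7.4.6.5 plans medication covariates that include post-randomization use; section 8.3 has no model for them, and adjusting for them between arms could bias the effect in either direction

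*Combined protocol and SAP*

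**What the plan says.** Section 7.4.6.5 says of concomitant medication that it "will be collected at baseline and regularly throughout the study to serve as covariates during analysis". The same sentence gives a second purpose, monitoring participants' health. The section also excludes people already on approved cessation medication, and allows, without requiring, withdrawal of someone who starts an interfering medicine during the double-blind phase.

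Randomization is at Visit 2 (Day 0, section 7.2.2). The Time & Events Table in section 7.1 has concomitant medication at every contact after that. Section 7.2.4, for Visit 3, reads: "Adverse events will be documented, and any concomitant medication changes will be recorded".

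Section 8.3 gives the whole analysis: "Paired sample t-tests (or nonparametric Wilcoxon Rank-Sum tests) will be used to examine changes in the outcome measures" from baseline. Section 10.7 repeats it. Neither names a covariate, a model or a contrast between arms.

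Section 1.1 hypothesizes that "smoking cessation will be greater in subjects assigned to a random nicotine delivery regimen", compared with steady state or placebo. The primary endpoints in section 1.2 are the "percent reduction in the number of cigarettes smoked and the accompanying percent reduction in exhaled carbon monoxide (CO) levels".

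**The concern.** A covariate in a randomized comparison should be fixed before treatment can influence it. Medication started after Day 0 is not. Section 11.0 itself describes two routes from the films to medication use. One is side effects: "Excess nicotine can cause mild symptoms such as nausea, dizziness, diarrhea, rapid heartbeat, heartburn, and hiccups". The other is withdrawal, which it expects may be worse on placebo. A third is plausible though not stated: someone who fails to quit may start a cessation aid, so that medication follows from the outcome.

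Where such a route exists and medication use is also tied to smoking, holding medication constant no longer estimates the effect of assignment, which is what section 1.1 asks about. Section 8.3 cannot answer that question as written, so some between-arm analysis will have to be added. Section 7.4.6.5 is then the only text saying what to adjust for. It leaves open which medicines, time points, endpoint and model are meant, which allows choices after the data are seen.

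**Working it through.** **Design figures.** Three arms of 15 (section 8.2) give 3 × 15 = 45, which agrees with section 8.1. The plan states no effect size, SD, alpha or power, so there is no planned effect to reproduce. Every effect and medication rate below is an assumption.

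**Algebra.** Let Δ be the difference in medication use (random minus placebo), and b the fitted coefficient of medication in a linear model with arm and medication. By least squares,

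unadjusted effect = adjusted effect + b × Δ, so the shift from adjusting = −b × Δ.

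The shift is zero if Δ = 0 or b = 0. If medication goes with a poorer outcome (b < 0), the shift takes the sign of Δ: toward no difference when the random arm uses less medication, away from it when that arm uses more.

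**Simulation 1.** Outcome y = 0.50 × arm + N(0,1), higher being better. Medication: logit P = b0 − b1 × y + g × arm. True effect 0.50 SD.

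| b0, b1, g | Medication, placebo vs random | Adjusted effect | Shift |
|---|---|---|---|
| −1.5, 1, 0 | 22% vs 16% | 0.44 | −0.06 (−12%) |
| −1, 1, 0 | 30% vs 22% | 0.43 | −0.07 (−14%) |
| −1, 1.5, 0 | 33% vs 22% | 0.38 | −0.12 (−24%) |
| −1.5, 0.25, 0 | 19% vs 17% | 0.495 | −0.005 (−1%) |
| −1.5, 0.5, 0 | 19% vs 16% | 0.483 | −0.017 (−3%) |
| −1.5, 1, 0.5 | 22% vs 22% | 0.50 | 0 |
| −1.5, 1, 1.0 | 22% vs 30% | 0.57 | +0.07 (+14%) |
| −1.5, 1, 1.5 | 22% vs 40% | 0.65 | +0.15 (+30%) |

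The last adjusted effect is 0.64 or 0.65 depending on the run. In the row with g = 0.5 the two routes cancel: −1 × 0.50 + 0.5 = 0, so Δ = 0. If medication depends on arm alone (10% vs 25%), b = 0 and the adjusted effect is 0.50.

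**Simulation 2, a different mechanism.** The total effect is 0.80 with unit residual SD. Medication depends on arm and, in some scenarios, on an unmeasured cause shared with the outcome; it may itself lower the outcome by 0.5. Assumed use is 21–26% in the comparison arm and 5–26% in the active arm. Adjusted effects run from 0.67 to 0.80, a bias of about −17% to 0%. The bias is zero whenever the films do not change medication use, and also when use neither affects the outcome nor shares a cause with it. These scenarios never let the films raise use, so they cannot show the upward shift.

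**Scale.** With 15 per arm and an SD of 1, the standard error of a difference is √(1/15 + 1/15) = 0.365 SD. The largest shifts above are 0.12 / 0.365 = 0.33 and 0.15 / 0.365 = 0.41 of a standard error.

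**The case against.** The strongest objection is that the plan contains no estimate to bias. The tests in sections 8.3 and 10.7 have no covariate term and no between-arm effect. This stands, and it rules out saying that the planned analysis is biased. It does not remove the conflict: section 7.4.6.5 promises covariates that section 8.3 cannot use, and the objective needs a comparison that section 8.3 lacks.

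Secondly, the sentence in section 7.4.6.5 has two collection times and two purposes, so it could mean baseline values for adjustment and later values for monitoring. That is possible, but the sentence makes no such split. Its ordinary reading attaches both times to both purposes.

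Thirdly, cessation medication is excluded at entry (section 3.2), checked again at Visit 2 (section 7.2.2.4), and may lead to withdrawal if started later. The first two act before randomization. The third is discretionary, so users can remain in the data, and it covers only interfering medicines.

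Fourthly, the shifts are smaller than the sampling error with 15 per arm, and one binary covariate costs one degree of freedom. Both are true, and they limit the weight of the point. Sampling error does not excuse a bias that a sentence can prevent, and the number of covariates is not stated.

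A reader might also infer that adjustment would pull the random-versus-placebo difference toward zero. That holds only where the random arm uses less medication and use goes with a poorer outcome. The side effects in section 11.0 could raise use on nicotine films instead, and the shift then reverses.

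**Conclusion.** The point holds in conditional form. Section 7.4.6.5, on its ordinary reading, makes post-randomization medication an analysis covariate, and section 8.3 has no model to receive it. If it entered the between-arm comparison that the objective requires, the effect of assignment could be biased upward or downward.

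Under the assumed models with a true effect of 0.50 SD, the adjusted effect lies between about 0.38 and 0.65. There is no bias if the films leave medication use unchanged, or if use is unrelated to outcome. The documents fix neither sign nor size. They do not support a certain bias, a bias toward no difference, or any particular percentage. Baseline medication is a legitimate covariate, and recording later medication for safety is proper.

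**What to change.** **Section 7.4.6.5.** Limit covariates to values fixed before randomization: Visit 2 CPD and CO and, if wanted, named baseline medications. State that medication started after randomization is summarized by arm and not adjusted for. Recording for health monitoring stays as it is.

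**Section 8.3.** Specify the between-arm comparison of percent reduction in CPD and in CO, each adjusted only for its own baseline value. Keep participants who start a cessation aid in the analysis as randomized, and add one sensitivity analysis counting them as having no reduction. No reduction suits the listed endpoints better than non-abstinence, because abstinence is neither a primary nor a secondary endpoint.

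**Cost.** A few sentences across the two sections and one extra sensitivity analysis. All the data are already collected, and no clinical procedure changes. Section 8.3 has no between-arm model to edit, so its text must be written new.
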